Study intervention, TID ⁶		X	X	X				A staggered dosing approach will be used for the first 10 participants (up to the first IDMC safety review). Each RESP301 dose will be administered by intermittent inhalation to monitor the tolerability and response to RESP301 (see Sections 6.1 and 9.6). Where possible study intervention should be administered at approximately the same times each day At least 6 hours between 2 consecutive doses
AE/SAE review	X	X	X	X	X	X	X	
Concomitant medication review	X	X	X	X	X	X	X	
Pre Treatment oxygen / respiratory assessment ⁷	X	X	X	X				
SpO ₂ on room air (after at least 1 minute) prior to study intervention administration and immediately at the end of nebulization ⁶		X	X	X				See Section 8.1.2

Procedure	Screening (up to 48 hours before Day 1 ¹)	Intervention Period			Early withdrawal	Efficacy follow-up (Day 14) ² (± 2 days)	EoS efficacy and safety follow-up (Day 28) ² (± 2 days)	Notes
		Day 1 ¹	Daily while hospitalized	Day 10 / hospital discharge				
Modified WHO ordinal scale	X	X	X	X		X	X	See Section 8.1.1
NEWS 2 assessment ⁷		X	X	X				Prior to study intervention in the morning. See Section 8.1.3

Abbreviations: AE=adverse event; aPTT= activated partial thromboplastin time; CBC=complete blood count; Chem 7=blood chemistry panel (sodium, potassium, chloride, bicarbonate/CO₂, blood urea nitrogen, creatinine, glucose); CV=cardiovascular; ECG=electrocardiogram; IDMC=Independent Data Monitoring Committee; LFTs=liver function tests; mHb=methemoglobin; PT/INR=prothrombin time/international normalized ratio; RT-PCR=reverse transcription-polymerase chain reaction; SAE=serious adverse event; TID=three times daily.

1. Screening and randomization may be on the same day, providing all eligibility criteria are met.
2. For participants who are already discharged at either the Day 14 or Day 28 (EoS) follow-up, there will be a phone call to check AEs/SAEs, concomitant medications, and modified WHO ordinal scale. At EoS, safety laboratory tests (nitrite and mHb only) and weight will be collected for participants in hospital only.
3. COVID-19 infection must be confirmed and documented in chart with a positive result on a validated test.
4. At Screening: CBC, chem 7, mHb, LFTs, and coagulation (PT/INR, aPTT).
On Day 1, Day 3, Day 7 and Day 10, or early withdrawal: CBC, chem 7 (per SOC), and mHb.
On Day 28: nitrite and mHb (participants in hospital at EoS only).

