5. Vital signs: temperature, heart rate, blood pressure, respiratory rate. Vital signs to be repeated as per SOC during treatment period.
6. Study intervention comprises the following procedures which are to be done in order and as quickly as possible:
 - a. Discontinuation of supplemental oxygen administration where applicable *
 - b. Close participant oversight by trained health care professional until SpO₂ is stable on ambient air after one minute at least *
 - c. Recording of SpO₂ * pre-nebulization on ambient air
 - d. Preparation of the admixture of RESP301 (to be done no longer than 5 minutes before administration)*
 - e. Administration of the nebulization via a vibrating mesh nebulizer while monitoring SpO₂ and heart rate (alarms set to 89% and 120 beats / min, or as indicated by the Investigator, for stopping study intervention administration and resuming supplemental oxygen where applicable) * If the participant is unable to tolerate nebulization without supplemental oxygen, nasal oxygen may be administered during nebulization.
 - f. Discontinuation of nebulization 20 minutes after preparation of admixture, or no product left in the device, whichever comes first *
 - g. Recording of SpO₂ * post nebulization on ambient air
 - h. Resuming supplemental oxygen where applicable*
 - i. Participant oversight until SpO₂ is stable *
 - j. Recording of SpO₂ *

* for participants on active treatment arm only
7. Participant remains on supplemental oxygen if applicable, and measurements made of respiratory rate, heart rate and SpO₂ and a record of oxygen flow level including mode (nasal cannula, mask)

2 Introduction

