2.2.3 Overall Benefit: Risk Conclusion

Taking into account the measures taken to minimize risk to participants in this first-in-man study, the potential risks identified in association with RESP301 are justified by the anticipated benefits that may be afforded to participants with COVID-19.

3 Objectives and Endpoints

Table 3-1 Objectives and Endpoints

Objectives	Endpoints
Primary	

 To evaluate efficacy of RESP301 in preventing progression of hospitalized COVID-19 participants at level 3 or 4 in the modified World Health Organization (WHO) ordinal scale into higher levels. 	
 Proportion of participants who progress by at least one level higher on the modified WHO ordinal scale by Day 14
Key Secondary	

 To assess the effect of RESP301 as measured by room air SpO₂ 	
 Change in room air SpO₂ from baseline over time

 To assess the effect of RESP301 as measured by the National Early Warning Score (NEWS) 2 symptom score 	
 Change in NEWS 2 symptom score from baseline over time

 To assess the treatment response on clinical status 	
 Change from baseline on the modified WHO ordinal scale at each visit up to Day 28 Time to improvement of at least one level lower on the modified WHO ordinal scale Time to progression of at least one level higher on the modified WHO ordinal scale
Additional Secondary	

 To assess the treatment response on clinical status 	
 Time to hospital discharge Incidence of mortality by Day 28
Safety	

 To assess the overall safety profile of RESP301 in COVID-19 participants 	
 Clinical safety laboratory measurements Physical examinations

Objectives	Endpoints
	
• Vital signs• Concomitant medications• Counts and cumulative incidence of:
○ Adverse events (AEs)○ Serious adverse events (SAEs)○ Severe AEs

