9.2 Sample Size Determination

A total of 300 hospitalized participants with confirmed COVID-19 will be randomized 2:1 to receive RESP301+SOC (200 participants) or SOC alone (100 participants).

The comparison between the treatment arms for the primary endpoint will have approximately 80% power and alpha level 0.025 (one-sided) to demonstrate significant reductions (15% versus 30%) of the primary endpoint between RESP001+SOC and the Control arm (SOC), a 50% relative reduction for the proportion of participants who progress by at least one level on the WHO ordinal scale (see definition of the primary endpoint).

Two interim analyses are planned (see Section 9.5 for details):

1. The first IDMC interim analysis will take place after the first 60 participants have completed Day 10 of the study to evaluate whether the study can be stopped for futility based on change from baseline in room air SpO₂. For a final decision to stop the study for futility the results on other endpoints will be considered as well.
2. The second interim analysis will take place after 150 participants have completed Day 14 post-randomization based on event rate for the primary endpoint. The purpose of the second interim analysis will be futility as well as a potential sample size re-estimation in case the actual results differ from the original assumptions.

In addition to the review of efficacy data, safety will be assessed at each of the interim analysis by the IDMC. Further details are provided in Appendix 5.

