9.5 Interim Analyses

Two interim analyses will be performed.

1. The first analysis will be conducted when about 60 participants (40 participants in the RESP301+SOC arm and 20 participants in the SOC arm) have completed the Day 10 assessment. The purpose of this analysis is to evaluate efficacy of RESP301 with the application of a futility criterion based on the results on SpO₂ change from baseline on Day 10. The following futility criterion will be used for this first interim analysis:

If the difference in the percentage of participants with at least a 2% improvement in SpO₂ between both treatment arms is less than 5%, benefit of RESP301 treatment is not expected. For a final decision to stop the study for futility the results on other endpoints will be considered as well.

As no other modification of the study at the time of the first interim analysis is considered, no adjustment of the alpha level is required.

2. The second interim analysis will be conducted after 150 participants (100 participants in the RESP301+SOC arm and 50 participants in the SOC arm) have completed the Day 14 assessment. The purpose of this analysis is the assessment of futility or a sample size re-estimation in case the actual results differ from the original assumptions for the power calculations of the study, related to the percentage of participants meeting the primary endpoint in the control arm and/or the relative treatment benefit achieved in the RESP301+SOC arm compared to the SOC arm.

To account for the multiple testing due to the second interim analysis an adjustment for the type I error alpha will be applied using the Haybittle-Peto approach which would spend one sided alpha=0.0005 at the second interim analysis and leave one-sided nominal alpha of 0.0249 for the final analysis. The futility criterion for the second interim analysis will be based on the conditional power (CP) for the final results based on the assumption that the remainder of the study will follow the same trend as observed in the interim analysis. If CP at the time of the second interim analysis is less than 20% consideration will be given to stop the study for futility. At the same time sample size re-estimation will be performed to achieve 80% power at the end of the study. The methodology for the adjustment and the procedure to maintain the type I error level will be described in greater detail in the SAP.

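### Room-air SpO₂ is tied to dosing steps that apply to the active arm only, yet the first-interim futility rule and a key secondary endpoint compare it between arms

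*Protocol*

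**What the plan says.** All references are to the current version of the protocol, which admits WHO levels 3 and 4.

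**Collection.** The Section 1.3 schedule has a separate row for SpO₂ "on room air (after at least 1 minute) prior to study intervention administration and immediately at the end of nebulization", marked for Day 1, daily in hospital, and Day 10 or discharge. The row has no arm label but is keyed to footnote 6. Steps a to j of footnote 6 all carry an asterisk, defined as "for participants on active treatment arm only". They include stopping supplemental oxygen (a), recording SpO₂ "pre-nebulization on ambient air" (c) and the post-nebulization ambient-air reading (g). Footnote 7, which belongs to the pre-treatment oxygen/respiratory assessment, carries no asterisk: "Participant remains on supplemental oxygen if applicable, and measurements made of respiratory rate, heart rate and SpO₂", together with oxygen flow and mode. Section 8.1.2 refers to the schedule for pulse oximetry and describes an oxygen hold only as a step before study drug is given.

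**Analysis.** Section 9.2 plans a first-interim assessment of "futility based on change from baseline in room air SpO₂". Section 9.5 describes "a futility criterion based on the results on SpO₂ change from baseline on Day 10" in about 40 active and 20 control participants. The signal for futility is a between-arm difference below 5% in the share of participants with at least a 2% improvement in SpO₂. Table 3-1 (Section 3) and Section 9.4.3 list "Change in room air SpO₂ from baseline over time" as a key secondary endpoint.

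**The concern.** The analysis needs the same variable in both arms. The schedule gives sites an instruction to collect it in one arm only, at least for participants who are on oxygen. Level 4 is defined in Section 8.1.1 by the need for supplemental oxygen, so the gap falls on level-4 controls. Level-3 controls breathe room air, so their footnote 7 reading is already a room-air value.

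At stake are the only numerical rule at the first interim and the between-arm estimate for one key secondary endpoint. A SAP cannot repair this later, because readings that were never taken cannot be recovered.

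**Working it through.** **1. Is a room-air reading directed for a level-4 control anywhere?**

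| Place | What it directs | Reaches a level-4 control? |
|---|---|---|
| Section 1.3, room-air SpO₂ row | Reading before study drug and at the end of nebulization, per footnote 6 | No arm label, but a control has neither moment, and footnote 6 is restricted |
| Footnote 6, steps a, c, g | Oxygen off; ambient-air SpO₂ before and after nebulization | No: starred, active arm only |
| Footnote 7 | SpO₂ with oxygen left on if used | Yes, but not on room air |
| Section 8.1.2 | Oxygen held before study drug | No: tied to dosing |
| Sections 3, 9.2, 9.4.3 | Change in room-air SpO₂, as futility variable or endpoint | Needed in both arms |

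No current instruction produces a room-air value for a control on oxygen.

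**2. Controls left at the first interim.** Input from Section 9.5: 20 controls. The level-4 share s among controls at the reading is not stated, so it is an assumption. Controls with a room-air value = 20 × (1 − s):

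- s = 25%: 20 × 0.75 = 15
- s = 50%: 20 × 0.50 = 10
- s = 75%: 20 × 0.25 = 5
- s = 90%: 20 × 0.10 = 2
- s = 100%: 0, and no room-air comparison is possible

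Controls who change level are also affected. One who improves from level 4 to level 3 has an on-oxygen baseline and a room-air follow-up. One who worsens from 3 to 4 has the reverse.

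**3. Loss of precision if those controls are dropped.** SE of the difference in responder shares, with both shares assumed near 50%: √(0.25/40 + 0.25/n_control).

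- n = 20: √(0.00625 + 0.0125) = 0.137
- n = 10: √(0.00625 + 0.025) = 0.177
- n = 5: √(0.00625 + 0.05) = 0.237

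**4. Effect on the futility signal.** This is the exact binomial probability that the observed difference is below 5 points, with 40 active participants. The responder rates are assumptions, since the protocol gives none.

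| True rates, active vs control | 20 controls | 15 | 10 | 5 | 2 |
|---|---|---|---|---|---|
| 60% vs 40% | 11% | 15% | 18% | 25% | 26% |
| 70% vs 40% | 2% | 4% | 7% | 13% | 17% |

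These figures show only the loss of controls. The remaining comparison would also set level-3 and level-4 active participants against level-3 controls alone.

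**5. Substituting on-oxygen control readings.** The protocol gives nothing from which to size or sign the resulting error. As a sensitivity check, take 60% vs 40% with all 20 controls, where the signal probability is 11%. If the mismatch moved the apparent control responder rate up 10 points to 50%, the probability would be 32%. If it moved it down 10 points to 30%, the probability would be 2%. The signal can shift materially either way.

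**6. Sample size.** The planned 300 is not in question. A two-proportion calculation (30% vs 15%, 2:1, one-sided 0.025, 80% power, continuity-corrected) gives 97 controls and 97 × 3 = 291 in total. This point changes neither that figure nor alpha.

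**The case against.** Several objections deserve weight.

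- **The row has no arm label.** It stands apart from the study-intervention row, and the Amendment 1.0 history records that an ambient-air reading was meant for both groups. This is fair as evidence of intent, and it makes the problem a contradiction rather than a deliberate choice. It does not supply an instruction: the row points to footnote 6 and is timed by events a control never has. The amendment history describes superseded text, so the finding does not rest on it.
- **Section 9.5 says SpO₂, not room-air SpO₂.** A result could therefore be computed from footnote 7 in both arms. That is possible, but Section 9.2 names room air for the same decision, and the key secondary endpoint names it too. The two sections would still have to be reconciled.
- **The rule is non-binding.** Sections 9.2 and 9.5 require other endpoints to be considered, and Appendix 5 calls the rule non-binding guidance. This stands and limits the consequence.
- **Details are left to the SAP and DMC Charter.** This holds for computation, but not for readings the schedule does not collect.

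A reader might also infer that the mismatch works against RESP301 and could stop the trial wrongly. The documents do not support a direction. The criterion is a responder share on change from baseline, not a comparison of levels, so a constant on/off-oxygen offset within a participant cancels. Controls on oxygen may also start from a supported baseline with less room to rise, which would favour RESP301. Nor can one say that all 20 interim controls lack a value: that is an upper bound, reached only if every control is at level 4, while level 3 is eligible.

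**Conclusion.** The point holds as an internal contradiction between the schedule (the room-air row and footnotes 6 and 7, with Section 8.1.2) and the analysis (Sections 3, 9.2, 9.4.3 and 9.5). Followed as written, controls on oxygen have no room-air SpO₂. The first interim then keeps between 20 controls (none at level 4) and 0 (all at level 4), or it compares two different measurements with a bias of unknown sign and size. The key secondary endpoint has the same gap.

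The size depends on the unstated level-4 share and on assumed responder rates. At an even level 3/4 split and 60% vs 40% responders, dropping the affected controls raises the chance of a false futility signal from 11% to 18%. The signal does not by itself stop the trial, and the primary endpoint (progression on the WHO scale by Day 14) is untouched. It should still be settled before the first interim, because missing control readings cannot be recovered afterwards.

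**What to change.** Before the first interim, reconcile the room-air SpO₂ row and footnotes 6 and 7 with Sections 3, 9.2, 9.4.3 and 9.5. The SpO₂ variable should be the same measurement, at matched pre-dose timing, in both arms. Sections 9.2 and 9.5 should name it identically.

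This can be done without changing care. Define the futility criterion and the key secondary endpoint on what footnote 7 and Section 8.1.2 already record in both arms: SpO₂ with concurrent oxygen flow or FiO₂, for example the ratio SpO₂/FiO₂. Use only the pre-dose reading in the active arm. The 2% responder definition must then be restated on that measure, and the 5-point threshold confirmed for it.

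The cost is wording in the schedule, the endpoint table and the interim section, with no new data. The drawback is noise, because Section 8.1.2 leaves FiO₂ measurement to site practice.

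Whether oxygen may be interrupted in controls to obtain a room-air reading is a clinical decision for the sponsor and is not proposed here.

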2.1 Background

Coronavirus disease 2019 (COVID-19) is a respiratory illness caused by a novel coronavirus (SARS-CoV-2). COVID-19 was first described in Wuhan, China, in December 2019 and is now a global pandemic (Matos et al, 2020). Most of those affected have milder illness (80%), 15% will be severely ill (require oxygen) and 5% will require intensive care unit care (Novel Coronavirus Pneumonia Emergency Response Epidemiology Team, 2020). Of those who are critically ill, most require early intubation and mechanical ventilation. Other complications include septic shock and multi-organ failure, including acute kidney injury and cardiac injury (Yang et al, 2020). Older age and comorbid diseases, such as chronic obstructive pulmonary disease (COPD), hypertension, and diabetes, increase risk of death (Huang et al, 2020; Zhou et al, 2020). The virus is highly contagious and spread via respiratory droplets, direct contact and, if aerosolized, airborne routes. The most common symptoms include fever, fatigue, dry cough, and shortness of breath.

A critical early component of innate host defense in the airway is the ability of respiratory epithelial cells to produce high levels of NO (Kao et al, 2001). NO functions as a signaling molecule in initiation of the inflammatory response to viruses, and also has direct antiviral effects (Folkerts et al, 1998). The airway epithelium has highly efficient nitric oxide (NO) synthetic machinery which is amplified in viral infection. Healthy human airway epithelium has abundant expression of the endothelial enzyme NOS II due to continuous transcriptional activation of the gene in vivo. Loss of NO synthesis in lung diseases predisposes individuals to increased virus/microbe infection (Xu et al, 2006).

The physiological roles of NO and the enzymatic pathways for its synthesis via NO synthase have been clearly established for many years (Tucker et al, 2007). In particular, NO has been demonstrated to have potent anti-microbial properties against a wide range of pathogens. An alternative non-enzymatic synthetic pathway for NO synthesis has been developed, which generates NO and related higher oxides of nitrogen (NOx) via the chemical reactions of acidified nitrite (Hardwick et al, 2001, Tucker et al, 1999). A solution of co-mixed NO/NOx and ascorbic acid (RespiNOS), delivered by nebulizer, was found to be safe and well tolerated in healthy volunteers (Tucker et al, 2007). Spectral investigations further confirmed that there were no potentially harmful moieties present in the solution. The study concluded that RespiNOS had potential for use as a broad-spectrum anti-microbial agent in patients with chronic bronchial sepsis such as bronchiectasis, COPD, and cystic fibrosis.

RESP301 is a NO-generating liquid designed to release NO in situ in the upper airways and deep in the alveolar spaces. RESP301 is an admixture solution of two precursor solutions mixed together at point of care for immediate inhaled administration via a CE-marked handheld nebulizer and has specific advantages (see below) over inhaled NO gas in treating patients with COVID-19 during the current pandemic. It has shown high in vitro activity against respiratory pathogens, both viral and bacterial.

Key advantages of RESP301 over inhaled NO gas are:

- RESP301 demonstrates powerful evidence in vitro as a broad-spectrum anti-microbial;
- Treatment is quick, easy and portable using a standard handheld nebulizer;
- The formulation is nebulized and forms a fine particle mist that settles on the lung surface, at the point of infection, and is therefore a more targeted approach;
- NO production continues in-situ post treatment;
- Because of the design of the formulation, production of NO₂ is negligible by virtue of the NO₂ being rapidly converted to a NO donor species.

The Sponsor has conducted a number of supportive in vitro studies to assess the activity of NO-generating solutions against major respiratory viruses responsible for infections in humans.

These studies include the following:

- In vitro studies to demonstrate the effects of RESP301 on SARS-CoV-2 replication
- In vitro study of RESP301 against influenza A (H1N1) and human rhinovirus
- Determination of the anti-viral efficacy of NO-releasing formulations against two strains of virus (influenza A virus [H1N1] and human rhinovirus 16)
- Anti-microbial activity of acidified nitrite solutions against intracellular drug sensitive and drug resistant *Mycobacterium tuberculosis* and *M. abscessus* infections
- Anti-microbial activity of RESP301 when used alone and in combination with antibiotics

Recent data from experiments at two independent laboratories using two different isolates of SARS-CoV-2 suggest that incubation with RESP301 for 36 to 48 hours reduced viral load to levels below the limit of detection of the assay at concentrations which were not associated with cytotoxicity. The limiting factor of the experiments was the slow growth rate of the viral controls; reduction in viral load was 2.2 and 4 Log₁₀ median tissue culture infectious dose (TCID₅₀).

[figure not shown]
Studies of inhaled nebulized sodium nitrite (AIR001) in healthy subjects and in patients showed that inhaled acidified nitrite produces dose proportional plasma pharmacokinetics without accumulation following repeated administration, with low systemic blood levels of nitrite and

methemoglobin (<3%) (Rix et al, 2015). Inhaled nitrite (AIR001) at doses up to 90 mg three times daily (TID) displayed a good safety profile and is well tolerated (Parsley et al, 2013; Simon et al, 2016), thus supporting the investigation of RESP301 in the clinical setting.

RESP301 delivers NO in a specifically focused way and with a unique mode of administration. It is an important evolutionary step in delivering NO that is more physiological and overcomes the technical difficulties and efficacy limitations of current NO gas therapy. Whereas inhaled NO gas has been used to treat patients with virus-induced acute respiratory distress syndrome and is being tested currently in COVID-19 patients, it focuses on increasing vascular permeability and is not sufficiently targeted at the infection, it is rapidly dispelled with exhalation and is oxidized in air to toxic NO₂. By comparison, RESP301 generates NO in a liquid environment that comes in direct contact with the virus and the virus-infected cells. As a result, RESP301 has a better targeted approach, and lower concentrations of NO are required, with a much more portable delivery system. An important environmental safety factor is that RESP301 produces negligible levels of NO₂ generated and exhaled NO.

In generating NO, RESP301 has at least three distinct mechanisms of action in fighting virus infection, two of which are common to many viruses and one is very specific to coronaviruses, such as SARS-CoV-2 (Figure 2-1).

Figure 2-1: Mode of Action of RESP301 Against SARS-CoV-2

1. Nitric oxide has a direct kill effect on the virus in the extracellular space. Nitric oxide-mediated nitrosylation of viral and host macromolecules appears to block viral replication and this has been demonstrated for several viruses (Saura et al, 1999; Basu et al, 1999). Enzymes, such as proteases (reverse transcriptases, and ribonucleotide reductase), vital for the life-cycle of the virus, are targets for NO nitrosylation (Benz et al, 2002; Colosanti et al, 1999).
2. In coronaviruses like SARS-CoV-2, NO specifically prevents membrane fusion of the S-protein (the spike protein that gives the virus its characteristic crown-like appearance) to the angiotensin-converting enzyme 2 receptor on the host cell.
3. Nitric oxide can attack the virus indirectly. Since viruses are non-living entities and do not have their own metabolism, they hijack the host cell's metabolic processes, and derive their energy and specific cellular substrates from the host cell. Nitric oxide suppresses the virus-induced hyperactivity in the host cell and thereby deprives the virus of its crucial supply chain.

RESP301 efficiently delivers with all three modes of action and is therefore considered an ideal candidate for clinical trials in COVID-19.

A detailed description of the chemistry, pharmacology, efficacy, and safety of RESP301 is provided in the Investigator's Brochure.

